#### To input text, click in the light grey area below.

Design: Randomized controlled trial.

**Population**: Adults with Hemoglobin A1C >8.0 measured at any point in the 12 months prior to enrollment, who have had at least one visit (Family medicine, behavioral health or other) with Lone Star Circle of Care within the past 12 months (in person or telehealth)

**Randomization:** Consented participants will be randomized to the intervention or control arm in a 1:1 ratio.

[figure not shown]
**Blinding:** Research staff involved in taking biomedical measurements will be blinded to participant status. Participants will complete surveys in person using a tablet or individual paper copy, thus research associates will remain blinded.

Time period: The study is divided into two parts.

- *Phase 1 (6 months)* is a randomized controlled trial testing the effect of telephone call-based empathetic engagement supported by caller-customized letters, together with small self-selected incentives (health tool) and caller-selected personal recognitions (small gifts selected based on the callers understanding of the participant), and low-literacy basic diabetes self-management information, against usual care. The primary outcome is Hemoglobin A1C (A1C) with repeated measures at baseline, 3 and 6 months.
- *Phase 2 (subsequent 6 months)* is the follow-up phase allowing us to *estimate* the 12 month longer term trajectory of A1C in Intervention and Control. To maximize the utility of the study to inform the most effective program design, participants in the control arm will receive the same opportunity to self-select health tool as the intervention arm received in Phase 1, but will make the choice during the 6

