#### To input text, click in the light grey area below.

Our primary outcome of interest is Hemoglobin A1C. However, the approach being used is modeled after a successful mental health intervention (Kahlon et al 2021) which showed depression can be improved with the type of empathy calls utilized in the current study.

To ensure that the effect of the empathy calls program on A1c can be assessed without confounding it with depressive mood in the first 6-month phase-I portion, we will rely on stratified randomization so that

approximately 50% (N=75) of the individuals in both the control and experimental group have a PHQ9  $\geq$ 5 at baseline and 50% of the individuals have PHQ9 <5 at baseline. With 150 individuals in each arm, three assessments for A1c, the primary outcome, and depression (PHQ9), secondary outcome, we have 80% statistical power with alpha = .05 to detect effects as small as f = .09, which is a small, standardized effect size, and have 90% power to detect effects as small as f = .10, also a small effect size, assuming only a moderate correlation for rank-order stability across time for each outcome of r = .30. This correlation is reasonable for A1c and is an underestimate for the typical correlation for PHQ9. Statistical power for the effect of interest increases as these correlations in the outcome measures goes up. Regarding correlations, we have 90% power to detect correlations as small as r = .26 and 80% power to detect correlations as small as r = .23 within each group (N = 150) at alpha = .05. These are fair to moderate effect sizes that bear on the power of any follow-up mediation analyses.

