We will test differences in the trajectory of A1c over the course of six-months with three assessments (baseline, 3- and 6-months) for those who receive empathy calls to support diabetes self-management versus those who do not receive these support calls. We will rely on linear mixed effect regressions with random terms to model individual differences in both the intercept and change terms, accounting for the clustering effect of shared lightly trained callers. We will predict these trajectories using the following person-level covariates: grouping indicator, terms to capture diabetic treatment type and dose, change in PHQ9 from baseline to 6-month depression. The cross-level interaction of grouping indicator with time will constitute the effect of interest. In addition, if change in depression predicts the person-specific slopes for A1c and does so more strongly for those in the intervention than control group, we would have evidence that depression management affects A1c course. Similar models will be constructed for the secondary outcome of depression, PHQ9 across three waves of data collection, with frequency/duration of support calls across those waves modeled as a time-varying covariate. Person-level covariates will include grouping indicator, terms to capture change in A1c from baseline to 6-months. If change in A1c predicts person-specific slopes for depression and does so more strongly for those in the intervention than control, we would have preliminary evidence that improved control of A1c affects course of depression, an unlikely outcome. The outcome of these mixed effect regressions will permit a preliminary estimate of the mediational role of depression on A1c management in phase-I. We will estimate those indirect effects using bootstrapped standard errors using the MPlus modeling framework for longitudinal change from baseline to 6-months. Healthcare utilization outcomes both self-reported and obtained from LSCC will be harmonized into a composite score of utilization. Depending on the distribution of each aspect of utilization (ER visits, hospitalization, PCP visits), we will construct models to predict differences between the intervention and control arm while covarying change in A1c and depression from baseline to 12-months.

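### Randomisation is stratified by baseline PHQ9, but no model uses the stratum and no within-stratum effect is planned, so a weak pooled PHQ9 or mediation result would be hard to interpret

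*Combined protocol and SAP*

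**What the plan says.** Section 5 (Data Analysis) and Section 15 (Sample size rationale) describe stratified randomisation in which about half of each arm (N=75) has PHQ9 of 5 or more and "50% of the individuals have PHQ9 <5 at baseline". The stated purpose is to keep the A1c effect from being confounded with depressive mood. Section 4 adds that "Consented participants will be randomized to the intervention or control arm in a 1:1 ratio".

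The same two sections give one power statement for both outcomes. It begins "With 150 individuals in each arm, three assessments for A1c, the primary outcome, and depression (PHQ9), secondary outcome" and continues "we have 80% statistical power with alpha = .05 to detect effects as small as f = .09" and "have 90% power to detect effects as small as f = .10", "assuming only a moderate correlation for rank-order stability across time for each outcome of r = .30".

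For PHQ9, Section 5 says "Similar models will be constructed for the secondary outcome of depression, PHQ9 across three waves of data collection". The person-level covariates are arm and change in A1c, and call frequency and duration enter as a time-varying covariate. For A1c they are arm, diabetes treatment type and dose, and change in PHQ9. The effect of interest is arm by time. A single bootstrapped indirect effect through depression is planned and is called preliminary. Baseline PHQ9 enters these models only as the first wave of the outcome or as part of a change score. No model has a term for the stratum, an arm by time by stratum term, or a within-stratum estimate. The Phase II text that speaks of analysing two groups separately refers to the trial arms, not the PHQ9 strata.

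The cut-off is not stated consistently. Sections 5 and 15 divide at ≥5 versus <5. The randomisation step in Section 11 (Procedure Description) divides at >5 versus <5, which leaves a score of exactly 5 in neither stratum.

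**The concern.** The trial is presented as a mental-health-first approach, built on an earlier calling programme "which showed depression can be improved with the type of empathy calls utilized in the current study". Completing the PHQ-9 is an entry condition (Section 13) precisely because of the stratified design. Yet about half the planned sample has few depressive symptoms to lose, and the plan averages over both halves without showing either.

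What is at stake is interpretation. A small pooled PHQ9 effect could mean that the calls do not relieve depression. It could equally mean that they do so in people with symptoms, while the other half had little room to move. The same ambiguity applies to the indirect effect on A1c, which uses PHQ9 change over the whole sample. If the stratum estimates are added only after a weak result, they will be read as a post-hoc subgroup search.

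**Working it through.** **1. The plan's own figure.** Inputs from Sections 5, 14 and 15: N = 300, two arms, m = 3 assessments, r = .30, alpha = .05. For the arm by time interaction in a repeated-measures F test, λ = f²·N·m/(1 − r), with 2 and 596 degrees of freedom.

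- 80% power needs f = .0868 (λ = .0868² × 900/.70 = 9.69).
- 90% power needs f = .0995 (λ = 12.73).

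These round to the stated .09 and .10, so the power statement reproduces. It describes a pooled effect in all 300.

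**2. The room to improve.** A baseline score of 0 to 4 can fall by at most 4 points. The largest possible mean fall in that stratum is 2.0 points if scores are spread evenly. Under two assumed skewed distributions, towards 0 and towards 4, it is 1.25 and 2.75 points.

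**3. Dilution of the estimate.** Let e be the effect in the ≥5 stratum and t the effect in the <5 stratum as a fraction of e. With a 50:50 split the pooled effect is e(1 + t)/2.

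- t = 0: the pooled effect is 50% of e.
- t = 0.2: it is 60% of e. This is what a proportional reduction gives with assumed stratum means of 2 and 10, since 2/10 = 0.2.

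This step does not depend on the SDs.

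**4. Power.** The documents give neither a PHQ9 SD nor a stratum effect, so the following are assumptions. Take e = 0.5, in units of the SD of 6-month change in the ≥5 stratum. Let k be the SD of change in the <5 stratum divided by that in the ≥5 stratum. The test is two-sided at 0.05, with no dropout.

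- Within the ≥5 stratum, 75 per arm: z = 0.5/√(2/75) = 3.06, power 86.5%.
- Pooled, 150 per arm: z = [e(1 + t)/2] / [√(2/150) × √((1 + k²)/2)].

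| k | pooled power, t = 0 | pooled power, t = 0.2 |
|---|---|---|
| 0.5 | z = 0.25/0.0913 = 2.74, 78% | z = 0.30/0.0913 = 3.29, 91% |
| 0.75 | z = 0.25/0.1021 = 2.45, 69% | z = 0.30/0.1021 = 2.94, 84% |
| 1.0 | z = 0.25/0.1155 = 2.17, 58% | z = 0.30/0.1155 = 2.60, 74% |

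**5. When pooling is the stronger test.** The ratio of stratum z to pooled z is √(1 + k²)/(1 + t). The pooled test wins once t exceeds √(1 + k²) − 1, which is 0.12 at k = 0.5 and 0.41 at k = 1.

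**6. The interaction test.** For the difference between strata, z = e(1 − t)/√[(2/75)(1 + k²)]. At e = 0.5, power is 78% to 58% (k = 0.5 to 1) if t = 0, and 59% to 41% if t = 0.2. With equal SDs and a ≥5-stratum effect just large enough for 80% power in that stratum (0.457 change-SD), the interaction has 51% power when t = 0.

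**The case against.** The strongest reply is that this is a choice of estimand. Eligibility rests on A1c, PHQ9 is a secondary outcome, and stratification was adopted for balance. The pooled contrast is a valid average over the enrolled population and was never meant to estimate a subgroup effect. That stands: the pooled analysis is not biased, and the stated f = .09 is not an arithmetic error.

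It is also fair that the floor limits how far an individual can improve but does not fix the arm contrast at zero. People below 5 can worsen over six months, and the calls may prevent some of that. Zero effect in that stratum is an assumption. Nor is the least favourable power figure the likeliest, because k = 1 sits awkwardly with a stratum near its floor. At k = 0.25 and t = 0, pooled power is 84%, close to the stratum's 86.5%. At k = 0.5 and t = 0.2 the pooled test is the stronger one.

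A reader might infer more than the documents support in three ways:

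- **That the stratum contrast is the only randomised evidence on the mental-health-first idea.** It is not. The planned pooled arm by time effects on A1c and PHQ9 are also randomised evidence. A difference between strata is effect modification by a non-randomised factor, and it does not isolate depression as the pathway.
- **That the plan's detectable effect can simply be doubled.** f = .09 corresponds to .09 × √24 = 0.44 outcome-SD of divergence by 6 months, which doubles to 0.88. That figure is in outcome-SD units and is not comparable with the change-SD example above.
- **That the ≥5 stratum should replace the pooled result or become the home of the mediation analysis.** Step 5 shows that pooling can be the better test. At 75 per arm, the correlation detectable with 80% power is r = .32, against the .23 stated for 150.

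What survives is narrower. The trial forms these strata and makes the PHQ-9 an entry condition to do so, yet it plans no estimate that would let a weak pooled result be understood.

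**Conclusion.** The point holds as a gap in the analysis plan, not as a flaw in the pooled estimate. Randomisation is stratified by PHQ9, no model contains the stratum, and only a pooled PHQ9 effect and one pooled indirect effect are planned. If the calls do little below PHQ9 5, the pooled estimate could be as low as 50% of the effect in people with symptoms.

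The effect on power is uncertain and can go either way. For an assumed 0.5 change-SD effect in the ≥5 stratum, pooled power is 78% to 58% with no effect below 5, and 91% to 74% with a 20% relative effect there. Within the ≥5 stratum it is about 86%. These figures rest on assumed SD ratios of 0.5 to 1, a 50:50 split and no dropout. The documents give no PHQ9 SD and no stratum effect. They also describe no enrolment quota, and stratified randomisation balances the arms without making the strata equal in size, so the actual split may differ.

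**What to change.** In Section 5:

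- Include the PHQ9 randomisation stratum in both the A1c and the PHQ9 models.
- Pre-specify an arm by time by stratum term for each outcome.
- Report the 6-month arm difference with its confidence interval in each stratum, beside the pooled result. Keep the pooled PHQ9 effect as the main secondary analysis.
- Label the stratum results as estimation, not as additional confirmatory tests.
- State that the power figure for PHQ9 refers to the pooled effect.
- Reconcile the stratum cut-off between Sections 5 and 15 and Section 11, so that a score of 5 falls in one defined stratum.

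The cost is plan wording and a few model terms on data already being collected, with no change to sample size or visits. The downsides are real but modest. Intervals are wider with about 75 per arm (half-width about 1.96 × √(2/75) = 0.32 change-SD within the ≥5 stratum), the interaction test has low power, and there are a few more estimates to interpret. A non-significant interaction should not be read as equal effects in the two strata.

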In this study we will use a randomized controlled trial to assess the impact of a 6-month long intervention of empathetic relationship building engagement with emotional and motivational support delivered telephonically for patients with diabetes at a Federally Qualified Health Center (FQHC). Telephone callers, lay people with light training on how to be empathetic and engaging in calls, will support participants' journeys on their own goals related to nutrition, exercise, sleep and medication adherence. They will not provide diabetes specific information, instead they will support people walking more, sleeping better, eating better and taking their medications. The impact of the program will be assessed primarily on Hemoglobin A1C levels and secondarily on depression and mental health at the end of the 6-month intervention, and in the following 6 months. Results will be compared to patients in the control arm that receive usual care. Participants will be recruited from our partner, an FQHC, Lone Star Circle of Care (LSCC) and include patients with Hemoglobin A1C of greater than 8.0 as measured at any point in the 12 months preceding enrollment.

- Chaoyang Li, Earl S. Ford, Tara W. Strine, Ali H. Mokdad. Prevalence of Depression Among U.S. Adults With Diabetes Diabetes Care Jan 2008, 31 (1) 105-107; DOI: 10.2337/dc07-1154
- Kahlon MK, Aksan N, Aubrey R, et al. Effect of Layperson-Delivered, Empathy-Focused Program of Telephone Calls on Loneliness, Depression, and Anxiety Among Adults During the COVID-19

Pandemic: A Randomized Clinical Trial. JAMA Psychiatry. 2021;78(6):616–622. doi:10.1001/jamapsychiatry.2021.0113

- Impact of a Telephonic Intervention to Improve Diabetes Control on Health Care Utilization and Cost for Adults in South Bronx, New York
- Bahman P. Tabaei, Renata E. Howland, Jeffrey S. Gonzalez, Shadi Chamany, Elizabeth A. Walker, Clyde B. Schechter, Winfred Y. Wu Impact of a Telephonic Intervention to Improve Diabetes Control on Health Care Utilization and Cost for Adults in South Bronx, New York. Diabetes Care Apr 2020, 43 (4) 743-750; DOI: 10.2337/dc19-0954

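### Section 5 declares no PHQ-9 or healthcare-utilisation arm comparison free of post-randomisation covariates, so the total programme effect on these secondary outcomes has no stated estimate

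*Combined protocol and SAP*

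**What the plan says.** Section 2 (Research Hypothesis) sets the question: "The impact of the program will be assessed primarily on Hemoglobin A1C levels and secondarily on depression and mental health". The time points it gives are month 6 and the half-year of follow-up. On the comparator it says: "Results will be compared to patients in the control arm that receive usual care". Section 4 (Measures) lists PHQ-9 and self-reported healthcare utilisation among the secondary outcomes, and its description of the control arm excludes telephone calls.

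For A1c, section 5 names the target: "The cross-level interaction of grouping indicator with time will constitute the effect of interest". For depression it says "Similar models will be constructed for the secondary outcome of depression, PHQ9 across three waves of data collection". Call exposure is part of the same description, which goes on "with frequency/duration of support calls across those waves modeled as a time-varying covariate". On terms that are constant within a person, section 5 then states: "Person-level covariates will include grouping indicator, terms to capture change in A1c from baseline to 6-months". For utilisation, section 5 says "we will construct models to predict differences between the intervention and control arm while covarying change in A1c and depression from baseline to 12-months".

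No other model in section 5 is declared as a between-arm comparison of either outcome. The MPlus analysis is described for indirect effects. In the phase-II paragraph, estimate (a) concerns A1c only, and estimate (b), which includes depression, is made separately within each group.

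**The concern.** Randomisation protects a comparison of arms as assigned. Calls are part of the intervention and are absent in controls. Change in A1c and change in depression are things the programme sets out to cause. An arm term conditional on any of these answers a different question from programme against usual care. It is the arm difference at a given number of calls (zero calls, if uncentred) or at a given amount of A1c or depression change.

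These covariates are legitimate for dose-response or mediation questions. The gap is that no arm comparison is declared without them. Followed literally, the plan would report arm terms for two named secondary outcomes that are not total effects. It would also leave the choice between adjusted and unadjusted results open until the data are seen. Depression matters particularly here, because section 2 describes the approach as putting mental health first.

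**Working it through.** **1. The stated power.** Section 5 gives 80% power at f = .09 and 90% at f = .10 for A1c and PHQ-9, with N = 300, m = 3 waves, r = .30 and alpha .05. For a group-by-time F test, lambda = f²Nm/(1 - r), with 2 and 596 degrees of freedom.

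- f = .09: lambda = .0081 × 900/.70 = 10.41, power 83.0%.
- f = .10: lambda = .01 × 900/.70 = 12.86, power 90.3%.

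The smallest f is .0868 for 80% and .0995 for 90%, so the stated figures reproduce after rounding. The between-groups version gives 56.7% and 65.7%, so the power statement describes a group-by-time test. It has no covariate terms.

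**2. Scale for PHQ-9.** Everything is put in outcome SD. The SD of change is √(2 × (1 - .30)) = 1.183. The SE of the arm difference in change is 1.183 × √(2/150) = 0.137. The total effect of -0.40 is assumed; its power without covariates is about 83%. No covariate relation below comes from the documents.

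**3. A1c change in the PHQ-9 model.**

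- *Main effect only.* With complete data, a covariate that is constant within a person does not touch the within-person time contrast. A three-wave generalised least squares check (150 per arm) gives a difference of zero.
- *With a time interaction.* Adjusted effect = total - b × d, where b is the slope of PHQ-9 change on A1c change and d is the arm effect on A1c change. Assume a within-arm correlation of .2 to .4 and d of -0.2 to -0.4 SD. The shift is .2 × .2 = 0.04 to .4 × .4 = 0.16 change SD, which times 1.183 is 0.05 to 0.19 outcome SD. So -0.40 becomes -0.35 to -0.21.
- *No true effect.* On the change-SD scale, SE = √[(2/150)(1 - ρ²)(1 + d²/4)]. At the upper corner this is √(.01333 × .84 × 1.04) = 0.108, and 0.16/0.108 = 1.48. Rejection is about 32% towards harm and 0.03% towards benefit. At the lower corner it is about 5% and 1%.

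**4. Calls in the PHQ-9 model.** Take total calls and a single change score. Calls are zero in controls, with mean μ and coefficient of variation c in the intervention arm. The arm term is total - βμ, where β is the slope on calls, and its SE is multiplied by √(1 + 1/(2c²)).

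- c = .3: factor 2.56, SE 0.350, power for -0.40 about 21%.
- c = .5: factor 1.73, SE 0.237, power about 39%.
- If benefit is unrelated to call count, β = 0 and the estimate is unbiased. If benefit is proportional to calls, βμ is the whole effect and the arm term is about 0.
- If benefit is proportional to calls and engagement also correlates .3 to .5 with PHQ-9 improvement, at c = .3 the term becomes .3/.3 = +1.0 to .5/.3 = +1.7 change SD, an apparent harm. The opposite association would push it the other way.

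The plan may instead mean calls per interval, which is the more natural reading. A three-wave calculation used the section 4 schedule with assumed take-up (about 15 connected calls in months 0-3 and 8 in months 3-6). The SE is only 5-8% larger. The estimate stays at -0.40 if benefit is unrelated to calls, and is -0.33 to -0.39 if benefit follows total calls, depending on the benefit model. With calls centred within arm and wave it is -0.40 with unchanged SE.

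Steps 3 and 4 are taken one at a time, whereas the described model carries both covariates.

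**5. Utilisation.** Units are utilisation SD, with a linear model as a stand-in, since section 5 makes the model depend on the distribution. Assume the two change scores correlate .3 with each other and .1 to .3 with utilisation, and that the arm effect on each is -0.2 to -0.4 SD. The shift in the arm term is 2 × corr × |d|/1.3, from 2 × .1 × .2/1.3 = 0.03 to 2 × .3 × .4/1.3 = 0.18. With no true effect, rejection is 6% to 39%, and at the upper corner almost all of it is upward (0.01% downward). With zero correlations there is no bias.

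**The case against.** The strongest reply is that section 5 describes a staged build. It speaks of models in the plural, calls them similar to the A1c models, and names group-by-time as the A1c effect of interest before turning to mechanism. The A1c-change question in the PHQ-9 text is phrased conditionally. The power figures match a covariate-free group-by-time test, and the MPlus model could contain an arm-to-PHQ-9 path free of A1c change. All this makes it plausible that a plain comparison was intended. None of it declares one: calls are added in the sentence that introduces the PHQ-9 models, and A1c change in the next.

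It is also right that A1c change as a person-level main effect leaves group-by-time unchanged. However, section 5 uses such covariates to predict trajectories and person-specific slopes, which implies the time interaction that does shift the arm term. Centring calls within arm and wave would likewise remove the call problem, but no centring is stated. Neither point helps the utilisation comparison, which is stated only with both change scores.

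Two limits stand. Section 2 names A1C, depression and mental health, not utilisation, so for utilisation the anchors are section 4 and the arm comparison in section 5 itself. And neither the sign nor the scale of a utilisation effect is given: callers may suggest contact with the clinic provider (section 4), so some visits could rise.

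**Conclusion.** The point holds as a gap in specification. For utilisation, the only declared arm comparison is at best a direct effect. For PHQ-9, the described model gives the total programme effect only under coding choices that the plan does not state.

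The size cannot be determined from the documents. It runs from none to substantial attenuation or apparent harm, and every figure above rests on assumed correlations, arm effects and call patterns.

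A reader might infer that the PHQ-9 result is certain to be biased. The documents do not support that, because harmless codings remain open. A reader might also infer a raised risk of false claims of benefit from the change-score terms. Under the assumed directions the error goes the other way: for PHQ-9 towards attenuation or apparent harm, and for utilisation upward, which is not harm for every type of visit. Nor is the stated power wrong; it reproduces.

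The primary A1c model is outside this point, but it carries "change in PHQ9 from baseline to 6-month depression", a covariate of the same kind, and should not be taken as cleared. Since these are named secondary outcomes and the repair is cheap, the change should be made.

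**What to change.** In section 5:

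- Declare the PHQ-9 arm-by-time comparison, giving the arm difference at 6 months, and at 12 months for the follow-up question in section 2.
- Declare the utilisation arm comparison.
- Adjust each only for baseline variables and the PHQ-9 stratification factor.
- Move call frequency and duration to a separate dose-response model within the intervention arm, stating whether calls are cumulative or per interval.
- Keep the A1c-change and depression-change terms in separate models labelled mediation or exploratory.

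This is a wording change. It needs no new data, visits or participants. The cost is a few more models to report, with the dose and mediation results marked as exploratory.

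### Mediation analysis: only bootstrapped standard errors are named; percentile bootstrap intervals from the same resamples would avoid a conservative test at almost no cost

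*Combined protocol and SAP*

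**What the plan says.** Section 5 (Data Analysis) plans mixed models for HbA1c and PHQ-9 over three waves. It says that their results "will permit a preliminary estimate of the mediational role of depression on A1c management in phase-I". The inference for the indirect effect is then given in one sentence: "We will estimate those indirect effects using bootstrapped standard errors using the MPlus modeling framework for longitudinal change from baseline to 6-months".

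No section states an interval type, a number of resamples or a rule for declaring an indirect effect present. No section says that the estimate divided by its standard error will be referred to a normal distribution, and none rules it out.

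Sections 5 and 15 give no power for the indirect effect. The nearest figures are for single correlations, such as "80% power to detect correlations as small as r = .23 within each group (N = 150) at alpha = .05", which the plan describes as relevant to later mediation analyses.

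**The concern.** An indirect effect is the product a × b. Here a is the effect of arm on the change in PHQ-9, and b is the slope of HbA1c change on PHQ-9 change. The sampling distribution of such a product is usually skewed when an effect exists. A bootstrap captures that shape, and a percentile interval uses it. A standard error reduces the resamples to one measure of spread, and its usual uses are symmetric around the estimate.

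Mediation through mood is the mechanistic question behind the mental-health-first approach in Section 2. A needlessly conservative test could miss a mediated effect that the same resamples would have shown.

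**Working it through.** **Inputs from the plan.** Size and waves: "With 150 individuals in each arm, three assessments for A1c, the primary outcome", so N = 300 and m = 3. Allocation is 1:1 (Section 4). Arm-by-time effect: "we have 80% statistical power with alpha = .05 to detect effects as small as f = .09". Correlation across time: ρ = .30. Detectable correlations: r = .23 (80% power) and r = .26 (90%), with N = 150. The plan does not state sidedness; two-sided alpha is assumed.

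**1. Reproduce the plan's figures.**
- Correlations, by Fisher z: power = Φ(atanh(r)·√(N − 3) − 1.96).
  - r = .23: Φ(0.2342 × 12.124 − 1.96) = Φ(0.88) = 81.0%.
  - r = .26: Φ(0.2661 × 12.124 − 1.96) = Φ(1.27) = 89.7%.
- Arm by time, by noncentral F with df 2 and 596: λ = f²·N·m/(1 − ρ).
  - f = .09: λ = .0081 × 300 × 3/.70 = 10.41, power 83.0%. The smallest f at 80% is .087, which rounds to .09.
  - f = .10: λ = 12.86, power 90.3%.

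The plan's figures reproduce.

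**2. Put the plan's effects on the two paths.** Treat f = .09 as a two-group difference in change: d = 2·√(λ/N) = 2·√(10.41/300) = .37. This a-path is a mean difference in residual SD units with arm coded 0/1. It is not a standardised path. The b-path is set to the plan's r.

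**3. Simulate.** There were 2000 trials per setting with 1000 resamples each, in a single-level model with normal errors and independent participants. The SE-based test (|ab/SE| > 1.96) and the 95% percentile interval use the same resamples. Monte Carlo error is about 1 point.

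| d, r | b-path from | SE-based | Percentile |
|---|---|---|---|
| .37, .23 (plan) | both arms | 74% | 87% |
| .37, .26 (plan) | both arms | 81% | 88% |
| .37, .23 (plan) | intervention arm | 49% | 69% |
| .37, .26 (plan) | intervention arm | 61% | 81% |
| .32, .16 (assumed smaller) | both arms | 39% | 61% |
| .32, .16 (assumed smaller) | intervention arm | 17% | 37% |
| .50, .30 (assumed larger) | both arms | 98% | 99% |
| .50, .30 (assumed larger) | intervention arm | 90% | 95% |

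A separate simulation of the first two rows gave 76% against 87% and 80% against 89%. Mean skewness of the bootstrap distribution was about 0.4 to 0.6 in these settings.

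The plan gives no dropout rate. With an assumed 20% loss (120 per arm), d = .37 and r = .23 give 60% against 78% (both arms) and 34% against 58% (one arm). The larger effects then give 95% against 97% and 80% against 90%.

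**4. Hand check of the percentile column.** The chance that both paths are individually significant should be close to it.
- a-path: Φ(√10.41 − 1.96) = Φ(1.27) = .897.
- b-path, both arms, r = .23: Φ(0.2342 × √297 − 1.96) = Φ(2.08) = .981. Product .88, against 87% simulated.
- b-path, both arms, r = .26: Φ(0.2661 × √297 − 1.96) = Φ(2.63) = .996. Product .89, against 88%.
- One arm, from step 1: .897 × .810 = .73, against 69%; .897 × .897 = .80, against 81%.

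**5. Type I error with one path zero and the other at the plan's value.**

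| Setting | SE-based | Percentile | Bias-corrected |
|---|---|---|---|
| d = 0, r = .23, both arms | 2.4% | 5.0% | 7.9% |
| d = .37, r = 0, both arms | 1.3% | 4.2% | 7.6% |
| d = 0, r = .23, one arm | 0.6% | 4.2% | 6.7% |

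The percentile gain is therefore not bought by exceeding 5%. Part of any gain from a bias-corrected interval would be.

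**The case against.** **The plan never states a normal test.** It says it will estimate indirect effects, and a bootstrapped standard error assumes no normality in itself. A reader might infer that the plan commits to treating the product as normal; the text does not say so. What remains is that the standard error is the only inference tool named, its ordinary uses are symmetric, and the better summary needs no additional data or resampling.

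**The loss is not large everywhere.** This stands. It depends on the size of the effects and on how many participants inform b. It also depends on how a is expressed. With arm coded 0/1, a = .30 and b = .20 give 46% against 70%. If arm is scaled to unit variance, the same numerals describe a much larger effect and give 89% against 93%. A reader might infer that a real mediated effect would probably be reported as absent. At the plan's detectable effects with both arms contributing, the SE-based test still has 74% to 81% power, so that inference fails there. It is closer to true only for smaller effects or when b rests on one arm.

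**Callers.** Section 5 accounts for clustering by caller in its mixed models, and it may be tempting to add resampling by caller to the change. Section 11 gives panels of 10 to 25, so 150 participants imply about 6 (150/25) to 15 (150/10) callers, and controls have none. That is few for a cluster bootstrap. A simulation of it, with assumed caller correlation of 0 or .05, gave percentile type I error of 5.5% to 9.5%, against 3.4% to 7.9% for the SE-based test. It would also be a different bootstrap, not the same resamples. The figures near 5% in the working hold for independent participants only.

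**The stakes are limited.** The plan calls the analysis preliminary, and any error is on the conservative side. This also stands and sets the weight of the point.

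**Conclusion.** The point holds in conditional form. If the bootstrapped standard errors are used as estimate/SE or estimate ± 1.96 SE, the mediation test is conservative. Compared with the percentile interval, it loses:
- about 7 to 13 points of power at the plan's detectable effects when both arms inform the b-path;
- about 20 points when only one arm does, or when effects are smaller;
- about 1 to 5 points for larger effects, with no dropout.

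These sizes assume two-sided alpha of .05, normal errors, independent participants, no further covariates and 150 per arm unless stated. The a-path is a mean difference in residual SD units.

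A reader might infer that the trial's main conclusion is at risk. It is not: the primary effect is the arm-by-time interaction, which does not use this method. The point is a cheap improvement to a preliminary secondary analysis.

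**What to change.** In Section 5, replace the bootstrapped standard errors with 95% percentile bootstrap confidence intervals, state the number of resamples, and give the rule. Possible wording: *Indirect effects will be reported with 95% percentile bootstrap confidence intervals based on [number] resamples; mediation will be declared only if the interval excludes zero.* Name the percentile interval specifically, because the bias-corrected interval exceeded 5% error in the check. Do not attach resampling by caller to this change.

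The cost is one sentence, with no new data. The small downside is that type I error rises from well below 5% to about 5%. The choice should be made before the analysis, so that the interval type is not selected after the results are seen.
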